EC	European Community
ECG	Electrocardiogram
eCRF	Electronic Case Report Form
EU	European Union
FCR	Fractional clearance rate
FDA	Food and Drug Administration

FSR	Fractional Synthesis Rate
FWA	Federal wide Assurance
GCP	Good Clinical Practice
GDPR	General Data Protection Regulation
GFAP	Glial Fibrillary Acidic Protein
GI	Gastrointestinal
GRAS	Generally recognized as safe
GWAS	Genome Wide Association Studies
HEK 293	Human embryonic kidney cells
HEENT	Head/ears/eyes/nose/throat
hERG	Human ether-a-go-go related gene
HbA1c	Hemoglobin A1C
HIPAA	Health Insurance Portability and Accountability Act
HPMC	Hydroxypropyl methylcellulose
H&Y	Hoehn and Yahr
ICH	International Conference on Harmonization
IEC	Independent Ethics Committee
IMP	Investigational Medicinal Product
IRB	Institutional Review Board
IUD	Intrauterine Device
IUS	Intrauterine Hormone Releasing System
kg	kilogram
MAD	Multiple Ascending Dose
MCI	Mild Cognitive Impairment
MDS	Movement Disorder Society
MDS-UPDRS	MDS-United Parkinson's Disease Rating Scale
MedRA	Medical Dictionary for Regulatory Activities
mg	milligram
min	minute
mITT	Modified Intent to Treat
mL	milliliter
MMRM	Mixed Model for Repeated Measures
MMSE	Mini-Mental State Examination
mRNA	Messenger Ribonucleic Acid
ms	milliseconds
N	Number of Subjects
NFL	Neurofilament Light
NG	Neurogranin
ng.h	Nanogram per hour
NIH	National Institutes of Health
NOAEL	No observed adverse effect level
OHRP	Office for Human Research Protections
p-tau	Phosphorylated tau
PD	Parkinson's disease
PGIC	Patients' Global Impression of Change
pH	Power of Hydrogen
PHI	Protected Health Information
PI	Principal Investigator

PID	Patient/Participant ID
PK	Pharmacokinetic
POC	Proof of Concept
PS1	Presenilin 1
QD	Once a Day
QID	4 Times a Day
QT	Interval seen in electrocardiogram (ECG) test
QTcf	Interval seen in QT (ECG) test
RA	Regulatory Authority
SAD	Single Ascending Dose
SAE	Serious Adverse Event
SAP	Statistical Analysis Plan
sAPPa	soluble APP alpha
sAPPb	soluble APP beta
SARS-CoV-2	Covid 19 Virus
SAS	Statistical Analysis System
SD	Standard Deviation
SH-SY-5Y	Human Derived Cell Line
SILK™	Stable Isotope Labeling and Kinetics
SNCA	Synuclein Alpha
SOC	Standard of Care / System Organ Class
SNRI	Selective Norepinephrine Reuptake Inhibitor
SSRI	Selective Serotonin Reuptake Inhibitor
sTREM	Soluble Triggering Receptor Expressed on Myeloid Cells
SUSAR	Suspected Unexpected Serious Adverse Reaction
$t_{1/2}$	Half-life
tau	Tau protein
TEAE	Treatment Emergent Adverse Event

1.0 PROTOCOL SYNOPSIS

PROTOCOL TITLE	A 6-month prospective, randomized, double-blind, placebo-controlled clinical trial investigating the efficacy, safety, and tolerability of two different doses of buntanetap or placebo in patients with early Parkinson's disease
STUDY DESIGN	
The study will be 6-month placebo-controlled and double-blinded: subjects, investigators and the sponsor will be blinded to the subjects' treatment.
 
Qualified subjects will be randomly assigned at a 1:1:1 ratio to one of three treatment arms: buntanetap 10 mg, buntanetap 20 mg, and placebo, through an Interactive Randomization System, after a screening period of up to 42 days.
 
MDS-UPDRS, PGIC, CGIS, WAIS coding, and MMSE will be assessed by clinicians who have successfully completed the requisite certifications/trainings for each assessment. All efforts will be made to ensure subjects will be assessed by the same clinician throughout the study. Participants should stop SOC Parkinson's medications 12 hrs before clinical visits to ensure clinical OFF-state during visit.

DURATION OF STUDY PARTICIPATION	Each subject will have up to a 42-day screening period, a baseline visit, followed by 6 months of treatment at home, followed by an in-clinic visit. The total duration of study participation will be 7-8 months.
SUMMARY OF INVESTIGATIONAL PRODUCT	Buntanetap 10mg, 20 mg, or placebo capsules, taken orally once a day for 6 months.
SUMMARY OF KEY ELIGIBILITY CRITERIA	
 • Diagnosis of idiopathic PD • Age 40 to 85 • MMSE 22-30 • Hoehn & Yahr =1,2,3 during ON-state & OFF-state < 2hrs per day
PRIMARY OUTCOME MEASURES	
Aim 1. Change from baseline to Month 6 in MDS-UPDRS Part II (OFF-state)
 
Aim 2. Safety and Tolerability

SECONDARY OUTCOME MEASURES	
Aim 1. Change from baseline to Month 6 in the sum of MDS-UPDRS Part II+III (OFF-state)
 
Aim 2. Change from baseline to Month 6 in the MDS-UPDRS Part III (OFF-state)
 
Aim 3. Change from baseline to Month 6 in the total MDS-UPDRS score (OFF-state)
 
Aim 4. Percentage of Responders with "Much Improved" or "Very Much Improved" on Participant Global Impression of Change (PGIC) (ON-state)
 
Aim 5. Change from baseline to Month 6 on Clinical Global Impression of Severity of illness (CGIS) (OFF-state)

EXPLORATORY OUTCOME MEASURES	Aim 1. Change from baseline to Month 6 in the plasma biomarkers measured

	Aim 2. Change from baseline to Month 6 in WAIS Coding Test (OFF-state) Aim 3. Change from baseline to Month 6 in MMSE (OFF-state) Aim 4. Pharmacokinetics (PK)
--	--

2.0 INTRODUCTION

Currently, there is no treatment available to stop or reverse the progression of Alzheimer's (AD) and Parkinson's disease (PD). Neurodegenerative diseases such as AD and PD share many common characteristics, including the central role of neurotoxic aggregating proteins in their pathogenesis. Amyloid β (A β) and tau aggregates (senile plaques and neurofibrillary tangles, respectively) have been traditionally associated with AD, while α -synuclein (α SYN) aggregates (Lewy bodies) have been associated with PD. However, it is becoming increasingly clear that all these proteins are involved in both diseases and that aggregation of one can lead to accumulation of another. Furthermore, in several studies of brains from older AD patients, a high percentage of all AD brains present mixed pathologies, such as Lewy body disease. Several clinical trials targeting just one (often A β) of the neurotoxic aggregating proteins have failed. Finally, other fragments of Amyloid β Precursor Protein (APP) have been implicated in AD pathology. Collectively, these facts point to the need for development of combination therapies that target multiple neurotoxic aggregating proteins simultaneously, if we are to have a good chance of at least halting disease progression.

Buntanetap has a unique mechanism of action, in that it inhibits the translation and, therefore, reduces the levels of several neurotoxic aggregating proteins both *in vitro* and *in vivo*, including α SYN, APP, its fragments, and tau. All three proteins have been implicated in the pathogenesis of PD. Furthermore, at older ages, there is a high incidence of PD patients with mixed pathologies, such as PD dementia. Therefore, it is reasonable to hypothesize that inhibiting expression of all three proteins should lead to a better efficacy outcome in PD patients than inhibiting just one.

α SYN, APP, and tau contribute to the progression of AD and PD in similar ways: they impair axonal transport and lower neurotransmitter and neurotrophic factor release, they cause inflammation, they form aggregates, and, finally, they lead to nerve cell death. In our *in vitro* and *in vivo* preclinical studies, buntanetap has normalized all those actions.

Preclinical data proves buntanetap's efficacy in restoring colonic motility in a human *SNCA^{A53T}* and *SNCA^{A30T}* transgenic (tg) mice models of early PD, in restoring memory and learning in an *APP/PS1* tg mouse model of AD, restoring axonal transport in DS trisomic mice, preserving memory, and learning in traumatic brain injury rats and in stroke mice, and preserving the retina in acute glaucoma.

Buntanetap's safety has been established in three Phase 1 clinical studies by [Maccecchini et al \(2012\)](#). Importantly, buntanetap normalized levels of α SYN, APP, and tau as well as inflammatory markers in the cerebrospinal fluid (CSF) of mildly cognitively impaired (MCI) subjects at a dose of 4x60 mg/day (Protocol QR12001).

Recently, we also tested buntanetap in the DISCOVER study at 1x60, 2x60 and 3x60 mg/day for up to 25 days to see if it changes the synthesis and degradation kinetics of A β in a stable isotope labelling kinetic (SILK) study. The DISCOVER study is conducted by the ADCS and was completed with 16 treated subjects (Protocol QR15001). The study officially finished in December 2021, with 7 patients treated in cohort 1 (1x60mg/day), 6 patients in cohort 2 (2x60mg/day), and 2 patients in cohort 3 (3x60mg/day). The CSF measurements of A β showed in a dose-dependent fashion that buntanetap slows the synthesis and lowers the total amount of A β synthesized by half. It also showed improvement in cognition as measured by the ADAS-Cog11 scale.

We recently completed a double Phase 2a study (ANVS-12003) in both early AD and early PD populations. In PD, 54 subjects were recruited and randomized into 0, 5, 10, 20, 40 and 80mg QD buntanetap for 25 \pm 2 days. CSF biomarkers were collected and analyzed. MDS-UPDRS and WAIS coding were tested. CSF biomarker results show that buntanetap lowered α SYN level, reduced inflammation (shown by GFAP, YKL-40, sTREM and Complement C3), preserved axonal integrity shown by neurofilament light (NFL) and improved synaptic density shown by neurogranin (NG). Although sample size was not powered to see efficacy, buntanetap improved PD subjects WAIS coding scores at all doses including 5mg QD. Buntanetap also improved PD subjects MDS-UPDRS Part II, III, IV and Total score.

In this study, we want to confirm buntanetap's efficacy in early PD subjects. During the dose-finding Phase 2a study, we saw a dose-response curve between 0 and 10/20 mg QD. Therefore, we decided to dose subjects with 10 and 20 mg QD.

2.1. OBJECTIVES

Study objectives include assessing buntanetap's efficacy and safety in early PD subjects.

Study drugs will be 10 mg, 20mg of buntanetap, or matching placebo capsules, taken once per day in the morning before food. Eligible subjects will be randomly assigned at a 1:1:1 ratio to one of the three treatment arms: buntanetap 10 mg, buntanetap 20 mg, and placebo, through an Interactive Randomization System, after a screening period of up to 42 days. The total duration of the study will be 7-8 months. MDS-UPDRS, PGIC, CGIS and WAIS coding will be assessed by clinicians who have successfully completed the requisite certifications/trainings for each assessment. All efforts will be made to ensure subjects will be assessed by the same clinician throughout the study. Participants should stop SOC Parkinson's medications 12 hrs before clinical visit to ensure clinical OFF-state during visit.

2.2. ENDPOINTS

Primary Endpoints:

1. Change From Baseline to Month 6 in MDS-UPDRS Part II (OFF-state)

Change in the Score from the MDS- Unified Parkinson's Disease Rating Scale (UPDRS) Parts II from Baseline to the End of Trial. MDS-UPDRS Part II (Motor experiences of daily living) has 13 items and the score ranges from 0–52, with higher score reflecting greater severity.

2. Safety and Tolerability

- Adverse Events (AE)
- Severity of AEs
- Drug related AEs
- AEs leading to study discontinuation
- Electrocardiogram findings
- Clinical laboratory test results
- Vital sign measurements
- Physical and neurological examination findings

Secondary Endpoints:

1. Change from Baseline to Month 6 in the sum of MDS-UPDRS Part II+III (OFF-state)

Change in the Sum of the Score from the Activities of Daily Living (ADL) Scale and Motor Examination in the MDS-UPDRS (Parts II+III, a UPDRS Subtotal) from Baseline to the End of Trial.

MDS-UPDRS Part II (Motor experiences of daily living) has 13 items and the score ranges from 0–52, with higher score reflecting greater severity MDS-UPDRS Part III (motor examination) has 18 items and ranges from 0-132, with higher scores reflecting greater severity. The sum of Part II+III will be 0-184, with higher scores reflecting greater severity.

2. Change from Baseline to Month 6 in the MDS-UPDRS Part III (OFF-state)

MDS-UPDRS Part III (motor examination) has 18 items and ranges from 0-132, with higher scores reflecting greater severity.

3. Change From Baseline to Month 6 in The Sum of MDS-UPDRS Total Score (OFF-state)

The MDS-Unified Parkinson's Disease Rating Scale (UPDRS) is a 50-item rating scale designed to assess Parkinson's disease-related disability and impairment. The scale comprises four parts: Part I evaluates mentation, behavior, and mood symptoms; Part II evaluates activities of daily living (ADL); Part III evaluates motor function; and Part IV evaluates complications of dopaminergic therapy. The Total score is the sum of the subscale scores for Parts I to III and ranges from 0 to 236, with higher scores reflecting greater severity.

4. Percentage of Responders with "Much Improved" or "Very Much Improved" on Participant Global Impression of Change (PGIC) (ON-state)

The PGIC is the participant-reported outcome. The qualitative assessment of meaningful change will be determined by the participant in response to the question, "Compared to your condition at the beginning of treatment, how much has your condition changed?" Scores are: 1=very much improved; 2=much improved; 3=minimally improved; 4=no change; 5=minimally worse; 6=much worse; and 7=very much worse. Percentage of responders with much improved and very much improved on PGIC scale will be assessed. PGIC will be taken at home while the subject is during ON-state (with their SOC for Parkinson disease).

5. Change From Baseline to Month 6 on Change on Clinical Global Impression of Severity (CGIS) (OFF-state)

The Clinical Global Impressions Scale on the severity of movement impairment as assessed by the site rater. Site raters will be asked: Considering your total clinical experience with the Parkinson disease population, how ill is the patient at this time? Answers were based on a 7-point scale, with 1=not assessed, 2= very mild, 3= mild, 4= moderate, 5= moderate severe, 6= severe, 7=extremely severe.

Exploratory Endpoints:

1. Changes From Baseline to Month 6 in The Plasma Biomarker Measured

Potential biomarkers to be measured in plasma are Neurofilament Light (NFL), Glial fibrillary acidic protein (GFAP) and TDP43.

2. Change From Baseline to Month 6 in WAIS Coding Test (OFF-state)

In the digital symbol coding test individuals are asked to record associations between different symbols and numbers within time limits. The Total score is the sum of all the correctly coded numbers.

3. Change From Baseline to Month 6 in MMSE (OFF-state)

The Mini-Mental State Exam (MMSE) is a 30-point test, widely used test of cognitive function.

4. Pharmacokinetics

The following PK parameters will be determined, as data permit: Area under the curve (AUC), Cmax, Tmax, t_{1/2}, and CL.

3.0 COMPLETED STUDIES

The following is a summary of the available information on buntanetap. Detailed information can be found in the current buntanetap Investigational Drug Brochure.

3.1. Summary of Non-Clinical Findings

In APP transgenic AD mice, buntanetap led to a decrease in APP levels, improved neuronal stem cell survival and increased levels of brain-derived neurotrophic factor (BDNF) (Marutle 2007; Kadir 2008, Lilja 2013). Chronic administration of buntanetap to APP transgenic mice totally prevented decline in memory and learning as well as in long-term potentiation at brain and plasma concentrations that are 10 times lower than originally published. These plasma levels are attainable with low oral dosing in humans (Teich 2018). In alpha-synuclein (αSYN) transgenic PD mice, buntanetap restored gut motility to normal and lowered αSYN in the brain and gut of the tg PD mice. Again, the efficacious levels were 10 times lower than originally published (Kuo 2019). In DS trisomic mice buntanetap fully restored axonal transport *in vitro* and *in vivo* (Chen 2021). In summary, buntanetap is a translational inhibitor of APP and αSYN and fully restores function at doses that are very low and very safe.

Buntanetap was not mutagenic or clastogenic as assessed by *in vitro* assays.

The cardiac electrophysiological properties of buntanetap tartrate were negative *in vitro* using human ether-a-go-go related gene (hERG) transfected human embryonic kidney cells (HEK 293). Buntanetap did not adversely affect the interval seen in an electrocardiogram (ECG) test (QT (or QTc) interval.

Toxicity studies in dogs showed brain toxicity (ataxia and tremors/twitching) and gastrointestinal (GI) toxicity at 30 mg/kg/day, which was dose-dependent and reversible. The no observed adverse effect level (NOAEL) was 20 mg/kg/day in dogs. Buntanetap readily crosses the blood-brain barrier. The signs/symptoms noted at high doses of buntanetap may be related to cholinergic manifestations. In *in vitro* assays, buntanetap showed minimal inhibition of AChE or BChE (Butyrylcholinesterase) activity, however, a metabolic product of buntanetap, N1-norposiphen demonstrated acetyl cholinesterase inhibitory activity (Yu 2013). There were no effects on the reproductive organs associated with 4-week exposure to buntanetap in male or female rats or dogs.

Repeat Oral dose Toxicity Study of buntanetap in male and female rats giving 10, 20 and 40 mg/kg for 26 weeks showed that NOAEL dose was 40 mg/kg for both male and female rats. Repeat Oral dose Toxicity Study of buntanetap in male and female dogs giving 5, 10 and 20 mg/kg for 39 weeks showed that NOAEL dose was 20 mg/kg for both male and female dogs.

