5.0 POTENTIAL RISKS AND BENEFITS OF INVESTIGATIONAL PRODUCT AND STUDY PROCEDURES

5.1. Risks and Benefits Associated with Buntanetap or Placebo

There are no benefits to the subjects other than receiving medical and selective functional and cognitive evaluations.

The clinical investigator must advise all potential subjects of the possibility of unexpected side effects and carefully evaluate each person exposed to Investigational Product for possible AEs.

Side effects to placebo are not uncommon but are obviously not due to a pharmacological agent as an industry standard placebo (inactive ingredients) will be provided. The placebo used for the study consists of standard (non-lactose) pharmaceutical excipients which are generally recognized as safe (GRAS), with no known side effects anticipated.

Buntanetap has been tested in animal safety studies. No adverse effects were observed in rats given doses up to 40 mg/kg/day for 26 weeks. Drug-related effects observed in dogs included severe tremors at \geq 20 mg/kg/day, ataxia and gastrointestinal erosion/ulcer/inflammation at \geq 30

mg/kg/day, convulsions at ≥ 60 mg/kg/day, and duodenal necrosis and death at 100 mg/kg (equivalent to a human dose of 3,350 mg).

In clinical studies to date, buntanetap has been well tolerated with single doses of 80 mg or less and QID doses of 60 mg up to 25 days. A higher single dose of 160 mg was associated with an increased incidence of nausea and vomiting, potentially cholinergic based side effects, which resulted in the decision not to test higher single doses. Aside from nausea and vomiting, which are well-known responses to treatment with AChE inhibitors, the only consistent pattern of AEs entailed dizziness/fainting, headache, and reduction in total serum protein. These effects were seen to varying degrees at all doses of buntanetap and also in the placebo group. There was a tendency, but no definitive pattern of increased incidence of AEs with increasing dose of buntanetap. There have been no SAEs in prior clinical studies with buntanetap.

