6.3. Safety and Tolerability Analysis

Safety and tolerability will be assessed with physical/neurological examinations, vital signs, clinical laboratory values, 12-lead ECG, use of concomitant medications, and AE reports. The frequencies of adverse events, serious adverse events, and laboratory abnormalities between the participants across the treatment groups will be compared.

Subjects who dropout during the initial 5 months at-home treatment period will be scheduled early discontinuation visit. Subjects who drop out after the initial 5 monthswill be scheduled for an end-of-trial visit. If 4 subjects are discontinued due to serious adverse events a safety review will be conducted without interrupting the study.

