6.11. Safety and Tolerability Analyses

Safety analyses will be conducted using data from the Safety Population.

Safety and tolerability will be assessed through TEAEs; hematologic, biochemical, and urinalysis laboratory parameters; physical/neurological examination findings; and vital signs measurements.

No formal statistical comparisons will be performed for safety endpoints.

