17.0 ADVERSE EVENTS OF SPECIAL INTEREST

Not applicable.

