# 4 Study Objectives and Endpoints

Objective	Endpoint	
Primary		
The primary objective is to assess efficacy and safety of buntanetap in	
 
Change from baseline to Month 6 in MDS- UPDRS Part II (OFF-state)
 
	
early PD subjects	Change in the Score from the Activities of Daily Living (ADL) Scale in the Movement Disorder Society-Unified Parkinson's Disease Rating Scale (MDS-UPDRS) (Part II, a MDS- UPDRS Subscale) from Baseline to Month 6. The MDS-UPDRS is a 50-item rating scale	
	designed to assess Parkinson's disease-related disability and impairment. The scale comprises four parts: Part I evaluates mentation, behavior, and mood symptoms; Part II evaluates ADL; Part III evaluates motor function; and Part IV evaluates complications of dopaminergic therapy.	
	Part II contains 13 questions which are to be completed by the participant (range 0-52). A higher score indicates more severe symptoms of PD.	
	2. Safety and tolerability	
	Adverse events (AE)	
	Severity of AEs	
	Drug related AEs	
	AEs leading to study discontinuation	
	Electrocardiogram (ECG) findings	
	Clinical laboratory test results	
	Vital sign measurements     Physical examination findings	

Objective	Endpoint	
Secondary		
Assess improvement on PD subjects' daily living, mobility, and complications	1.	Change from baseline to Month 6 in the sum of MDS-UPDRS Part II+III (OFF-state)
		Change in the Sum of the Score from the ADL Scale and Motor Examination in the MDS-UPDRS (Parts II+III, a MDS-UPDRS Subtotal) from Baseline to Month 6.
		Part II contains 13 questions which are to be completed by the participant (range 0-52). Part III contains 33 scores based on 18 items (range 0- 132). MDS-UPDRS Part II and III combined score equals the sum of Parts II and III (range 0-184). A higher score indicates more severe symptoms of PD.
	2.	Change from baseline to Month 6 in MDS- UPDRS Part III (OFF-state)
		Part III (motor function) contains 33 scores based on 18 items (Range 0-132). A higher score indicates more severe symptoms of PD.
	3.	Change from baseline to Month 6 in the sum of MDS-UPDRS Total score (OFF-state)

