#### 8.3.12 Adverse Events

Adverse events include but are not limited to:

- worsening or change in nature, severity, or frequency of conditions or symptoms present at the start of the study;
- Subject deterioration due to primary illness;
- intercurrent illness;
- drug interaction.

An abnormal laboratory value will only be reported as an AE if the investigator considers it clinically significant, or if it leads to the Subject being withdrawn from the study.

Symptoms and conditions present at the beginning of the study will be characterized, so that AEs can be defined as any new symptom, or any increase in frequency or severity of an existing symptom.

AEs will be coded according to the most recent version of the MedDRA system and will be tabulated by system organ class (SOC) and PT.

A TEAE is an undesirable event that is not present prior to medical treatment, or an already present event that worsens either in intensity or frequency following the treatment. Only TEAEs will be included in summary tables and non-TEAEs will be listed separately.

Relationship to clinical study treatment will be mapped according to the scheme below:

- Potentially related: will include all adverse events with a relationship rating of "definitely", "probably" or "possibly".
- Unlikely/not related: will include all adverse events with a relationship rating of "unlikely" or "unrelated".

An overall summary table will give

- number of events
- number of unique events
- number of subjects with at least one event

for:

- Overall summary of TEAEs
- Serious TEAEs
- Serious TEAE related to study drug
- TEAEs related to study drug
- TEAEs by severity according to Rheumatology Common Toxicity Criteria (RCTC) categories
- TEAEs leading to treatment discontinuation of study drug
- TEAEs leading to withdrawal from study
- TEAEs leading to death

The overall summary presentation will be repeated for:

- Severity categories
- TEAEs related to study drug

The total number and percentage of subjects with at least one TEAE and the total number of TEAEs will be presented by SOC and PT.

Frequent TEAEs are defined as any PT with ≥5% incidence in any of the treatment arms, which will be summarized by PT.

Deaths, other serious AEs (SAEs), and other significant AEs will be listed, these include the following TEAEs:

- SAEs leading to death
- SAEs not leading to death
- AEs for which action was taken with study drug
- AEs leading to withdrawal from study

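### Safety is a primary endpoint with a named cholinergic mechanism, but the SAP groups no cholinergic-type events across organ classes and gives no active-minus-placebo difference with an interval

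*Protocol*

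**What the plan says.** Protocol 2.2 lists "2. Safety and Tolerability" among the primary endpoints, with adverse events, their severity, drug-related events and events leading to discontinuation beneath it. SAP Section 4 agrees: "The primary objective is to assess efficacy and safety of buntanetap in" early PD subjects.

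On mechanism, Protocol 3.1 says of the dog toxicity that "The signs/symptoms noted at high doses of buntanetap may be related to cholinergic manifestations" and notes that a metabolite inhibits acetylcholinesterase. Protocol 3.2 states that the level of the N1-metabolite sets the highest tolerated dose. Protocol 5.1 calls the nausea and vomiting at 160 mg potentially cholinergic and says they ended escalation. It adds that, apart from these, "the only consistent pattern of AEs entailed dizziness/fainting, headache, and reduction in total serum protein", and that these effects also occurred on placebo.

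On analysis, Protocol 17.0 answers "Not applicable" for adverse events of special interest. SAP 8.3.12 plans treatment-emergent adverse event (TEAE) summaries overall and by system organ class (SOC) and preferred term, severity, relatedness, seriousness, treatment discontinuation, study withdrawal and death. It adds a frequency table: "Frequent TEAEs are defined as any PT with ≥5% incidence in any of the treatment arms, which will be summarized by PT".

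Protocol 6.3 says: "The frequencies of adverse events, serious adverse events, and laboratory abnormalities between the participants across the treatment groups will be compared". Protocol 6.11 says: "No formal statistical comparisons will be performed for safety endpoints".

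**The concern.** The sponsor has a specific hypothesis about what would limit tolerability, and the plan has no display aimed at it. Cholinergic-type effects can be coded in several organ classes (gastrointestinal, nervous system, cardiac, general). The multiple-dose study gives an example: its one premature discontinuation was a subject with nausea, vomiting, dizziness and feeling warm (Protocol 3.2). In a table by class and term, one such reaction is spread over several rows.

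Counts by arm also leave the reader to work out the excess over placebo and its uncertainty. A safety conclusion at 10 or 20 mg needs a statement of what excess the data rule out, and that takes an interval. The protocol describes earlier human exposure of about 25 days at most (5.1, and 2.0 for Phase 2a). Six months with 174 per arm is therefore much the largest and longest placebo-controlled safety experience it describes.

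**Working it through.** **No safety figure to reproduce.** The documents give no precision or power for safety and no adverse-event rates for this trial. The only input taken from them is 174 per arm (SAP 8.10.2). The efficacy power stated there reproduces (difference 3, SD 8, two-sided 0.025: 89.6% against the stated 90%) but does not bear on this point.

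**Assumptions.** Six cholinergic-type terms, each at 1.5% on placebo and 3% on one active dose, with 2% versus 4% as a second case. All 174 per arm are in the safety set. The interval is Agresti-Caffo: p̃ = (x+1)/(n+2), difference ± 1.96·√[Σ p̃(1−p̃)/(n+2)]. The result of interest is how often its lower limit is above zero.

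**Pooled rate for k independent terms:** 1 − (1 − p)^k.
- k = 4: 1 − 0.985⁴ = 5.9% versus 1 − 0.97⁴ = 11.5%.
- k = 6: 1 − 0.985⁶ = 8.7% versus 1 − 0.97⁶ = 16.7%.

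**Chance that the 95% interval excludes zero:**

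| Display | 1.5% vs 3% | 2% vs 4% |
|---|---|---|
| One preferred term | 8% | 14% |
| Four independent terms in one SOC row, nothing else in the row | 45% | 57% |
| Six-term group, independent | 61% | 74% |
| Six-term group, latent correlation 0.3 | 49% | 60% |
| Six-term group, latent correlation 0.5 | 41% | 50% |
| Six-term group, latent correlation 0.7 | 32% | 40% |

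The correlated rows keep each term's rate and link the terms within a subject through a normal copula. At 1.5% versus 3% the any-of-six rates become 7.7% vs 14.3%, 6.6% vs 12.1% and 5.3% vs 9.6%. The SOC row is shown for independent terms only, so it should not be compared directly with the correlated rows; correlation would lower it too.

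**The 5% table.** 0.05 × 174 = 8.7, so a term needs 9 subjects in an arm. At a true 3%, P(X ≥ 9) = 0.080 per term. For at least one of six independent terms, 1 − (1 − 0.080)⁶ = 39%. At a true 4% the figures are 26% and 84%.

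**What an interval would show.** Take five independent terms at 1% versus 3%. Expected counts for one term are 5 versus 2 subjects: risk difference 1.7 points, Newcombe 95% CI −1.6 to 5.5. Grouped, they are 25 versus 9 subjects: 9.2 points, CI 3.0 to 15.7.

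**The case against.** The case against is substantial, and much of it stands.

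- **Other tables exist.** A reader might infer that adverse events are counted only by class and single term. SAP 8.3.12 does not support that: severity, relatedness, seriousness, discontinuation, withdrawal and death are also summarised by arm.
- **Partial pooling is already planned.** The human effects that the protocol itself calls potentially cholinergic are nausea and vomiting, and the gastrointestinal row pools these with diarrhoea. SAP 8.4 summarises pulse and ECG variables and gives shift tables for tremor, gait and coordination. The DSMB reviews safety throughout and may ask for unblinded data.
- **Dizziness and fainting.** One might read these as part of an established cholinergic pattern. Protocol 5.1 sets them apart from nausea and vomiting and reports them on placebo too. Protocol 3.1 is hedged and concerns dogs at high doses.
- **Dose context.** Escalation stopped at 160 mg, and 80 mg was the no-effect level in the single-dose study. Protocol 4.1 puts pharmacological activity 8 to 16 times below cholinomimetic levels. This lowers the expected signal; it does not supply an estimate of excess.
- **Protocol 6.3 against 6.11.** A reader might see a contradiction. Both can hold if the comparison in 6.3 is descriptive. The wording is loose, and no method is given.
- **Recoverability.** Differences for overall, serious, related and discontinuation events can be calculated from the planned counts, and a cholinergic group could be assembled later from listed data. What would be lost is a list fixed without sight of treatment.

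These points narrow the gap without closing it. No planned table crosses organ classes for these events, and none gives a difference from placebo with an interval.

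**Conclusion.** The point holds as a cheap improvement. For a primary safety endpoint with a stated mechanism, the plan has no prespecified cross-class group and no estimate of excess over placebo.

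The size is illustrative: every event rate is assumed. At 1.5% versus 3%, a single term would be clearly separated from placebo in about 8% of trials. The six-term group would be in 61% under independence, or 32% to 49% with latent correlation from 0.7 to 0.3. The gain over a clean four-term class row (45%) is moderate under independence and depends on how far the terms co-occur and how many unrelated events dilute the row.

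The stronger inference that a cholinergic signal would go unseen is not supported: under the same assumptions with independent terms, at least one of the six reaches the 5% table in about 39% of trials. Nor do the documents support saying that the trial could not derive any excess over placebo. They support saying that the plan does not commit to reporting one.

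**What to change.** In SAP 8.3.12, define one group of cholinergic-type TEAEs by a list of MedDRA preferred terms settled on medical judgement before unblinding. For that group, and for any, drug-related, serious and discontinuation TEAEs, report each dose minus placebo as a risk difference with a 95% CI (Newcombe or Miettinen-Nurminen). Label these descriptive and give no p-values. Word Protocol 6.3 and 6.11 alike: descriptive estimates with intervals, no hypothesis tests.

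The cost is SAP and protocol wording plus one or two tables from data already collected, with no new visits or subjects. The downsides are that the intervals are not adjusted for multiplicity and that the list involves judgement; settling it while blinded contains the second.
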